## **8.5 FINANCIAL DISCLOSURE**

Investigators will provide the Sponsor with sufficient, accurate financial information in accordance with local regulations to allow the Sponsor to submit complete and accurate financial certification or disclosure statements to the appropriate health authorities. Investigators are responsible for providing information on financial interests during the course of the study and for 1 year after completion of the study (see definition of end of study in Section 3.2).

## **9. STUDY DOCUMENTATION, MONITORING, AND ADMINISTRATION**

### **9.1 STUDY DOCUMENTATION**

The investigator must maintain adequate and accurate records to enable the conduct of the study to be fully documented, including, but not limited to, the protocol, protocol amendments, Informed Consent Forms, and documentation of IRB/EC and governmental approval. In addition, at the end of the study, the investigator will receive the patient data, including an audit trail containing a complete record of all changes to data.

### **9.2 PROTOCOL DEVIATIONS**

The investigator should document and explain any protocol deviations. The investigator should promptly report any deviations that might have an impact on patient safety and data integrity to the Sponsor and to the IRB/EC in accordance with established IRB/EC policies and procedures. The Sponsor will review all protocol deviations and assess whether any represent a serious breach of Good Clinical Practice guidelines and require reporting to health authorities. As per the Sponsor's standard operating procedures,

prospective requests to deviate from the protocol, including requests to waive protocol eligibility criteria, are not allowed.

### **9.3 SITE INSPECTIONS**

Site visits will be conducted by the Sponsor or an authorized representative for inspection of study data, patients' medical records, and eCRFs. The investigator will permit national and local health authorities; Sponsor monitors, representatives, and collaborators; and the IRBs/ECs to inspect facilities and records relevant to this study.

### **9.4 ADMINISTRATIVE STRUCTURE**

This trial will be sponsored and managed by F. Hoffmann-La Roche Ltd. The Sponsor will provide clinical operations management, data management, and medical monitoring.

Approximately 20 sites globally will participate to enroll approximately 24 patients. Enrollment will occur through an IxRS.

Central facilities will be used for certain study assessments throughout the study (e.g., specified laboratory tests, biomarker and PK analyses), as specified in Section 4.5. Accredited local laboratories will be used for routine monitoring; local laboratory ranges will be collected.

A Safety Monitoring Committee will be employed to monitor and evaluate patient safety throughout the study.

### **9.5 PUBLICATION OF DATA AND PROTECTION OF TRADE SECRETS**

Regardless of the outcome of a trial, the Sponsor is dedicated to openly providing information on the trial to healthcare professionals and to the public, both at scientific congresses and in peer-reviewed journals. The Sponsor will comply with all requirements for publication of study results. For more information, refer to the Roche Global Policy on Sharing of Clinical *Study Information* at the following Web site:

[www.roche.com/roche\\_global\\_policy\\_on\\_sharing\\_of\\_clinical\\_study\\_information.pdf](http://www.roche.com/roche_global_policy_on_sharing_of_clinical_study_information.pdf)

The results of this study may be published or presented at scientific congresses. For all clinical trials in patients involving an IMP for which a marketing authorization application has been filed or approved in any country, the Sponsor aims to submit a journal manuscript reporting primary clinical trial results within 6 months after the availability of the respective Clinical Study Report. In addition, for all clinical trials in patients involving an IMP for which a marketing authorization application has been filed or approved in any country, the Sponsor aims to publish results from analyses of additional endpoints and exploratory data that are clinically meaningful and statistically sound.

The investigator must agree to submit all manuscripts or abstracts to the Sponsor prior to submission for publication or presentation. This allows the Sponsor to protect proprietary information and to provide comments based on information from other studies that may not yet be available to the investigator.

In accordance with standard editorial and ethical practice, the Sponsor will generally support publication of multicenter trials only in their entirety and not as individual center data. In this case, a coordinating investigator will be designated by mutual agreement.

Authorship will be determined by mutual agreement and in line with International Committee of Medical Journal Editors authorship requirements. Any formal publication of the study in which contribution of Sponsor personnel exceeded that of conventional monitoring will be considered as a joint publication by the investigator and the appropriate Sponsor personnel.

Any inventions and resulting patents, improvements, and/or know-how originating from the use of data from this study will become and remain the exclusive and unburdened property of the Sponsor, except where agreed otherwise.

## **9.6            PROTOCOL AMENDMENTS**

Any protocol amendments will be prepared by the Sponsor. Protocol amendments will be submitted to the IRB/EC and to regulatory authorities in accordance with local regulatory requirements.

Approval must be obtained from the IRB/EC and regulatory authorities (as locally required) before implementation of any changes, except for changes necessary to eliminate an immediate hazard to patients or changes that involve logistical or administrative aspects only (e.g., change in Medical Monitor or contact information).

**Appendix 1a**  
**Schedule of Assessments: Randomized Treatment Phase (Treatment Period)**

Assessments	Screening Day b –35 to –0	Study Days (±3 days) a											Early Withdrawal from Treatment or Discontinuation
		1 c	4	28 (Wk 4)	56 (Wk 8)	60 d	70 d	84 (Wk 12)	88	98	112 (Wk 16)	Unscheduled Visit e	
Informed consent	x												
Review eligibility criteria	x	x f											
Demographic data	x												
Pregnancy test g	x	x f		x f	x f			x f			x		x
Vital signs (BP and pulse)	x	x f	x	x f	x f			x f	x	x	x	x	x
ECG	x												x
Chest X-ray h	x												
Height	x	x		x	x			x			x	x	x
Weight	x	x		x	x			x			x	x	x
Tanner Stage	x												x
Medical history	x												
Physical examination i	x							x		x		x	x
PML neurologic examination j	x		x					x				x e	x
Hematology	x	x f		x	x f			x		x	x	x e	x l
ESR k	x			x	x			x			x	x	x
Chemistry	x	x f		x k	x f			x k		x	x	x e	x l
Urinalysis	x	x f			x f							x e	

**Appendix 1a**  
**Schedule of Activities: Randomized Treatment Phase (Treatment Period) (cont.)**

Assessments	Screening Day b – 35 to – 0	Study Days ( $\pm 3$ days) a												Early Withdrawal from Treatment or Discontinuation
		1 c	4	28 (Wk 4)	56 (Wk 8)	60 d	70 d	84 (Wk 12)	88	98	112 (Wk 16)	Unscheduled Visit e		
TB screen m	x													
Viral serology and detection tests n	x													
Saliva sample o		x												
Stool sample	x p	x q									x q		x q	
PK sampling (serum) r		x	x	x	x	x	x	x	x	x	x e		x l	
Anti-drug antibody sample (serum) r,s		x		x				x			x	x e		x l
Plasma sample (storage for post-study JCV antibody testing) t	x													
PUCAI or PCDAI u		x		x	x			x			x	x e		x l
Serum sample (CRP)		x f		x f							x	x e		x l
PD (receptor occupancy) flow cytometry sampling (whole blood) r		x	x		x			x		x	x		x	
Serum PD measures (MAdCAM-1) r		x	x		x			x		x	x	x		x
Colonic biopsy (CMV, if required)	x v											x e		

## Appendix 1a

### Schedule of Activities: Randomized Treatment Phase (Treatment Period) (cont.)

Assessments	Screening Day b – 35 to – 0	Study Days ( $\pm 3$ days) a												Early Withdrawal from Treatment or Discontinuation
		1 c	4	28 (Wk 4)	56 (Wk 8)	60 d	70 d	84 (Wk 12)	88	98	112 (Wk 16)	Unscheduled Visit e		
Concomitant medications		x	x	x	x			x	x	x	x	x	x	x
Adverse events	x	x	x	x	x			x	x	x	x	x	x	x
Randomization		x w												
Etrolizumab administration Q4W a, x		x		x	x			x						
Etrolizumab administration Q8W a, x		x			x									

ADA=anti-drug antibody; BP=blood pressure; CD=Crohn's Disease; CMV=cytomegalovirus; CRP=C-reactive protein; ECG=electrocardiogram; eCRF=electronic Case Report Form; ESR=erythrocyte sedimentation rate; HBc=HBV core antibody total; HBsAg=HBV surface antigen; HBV=hepatitis B virus; HCV=hepatitis C virus; JCV=John Cunningham virus; MAdCAM-1=mucosal vascular addressin cell adhesion molecule-1; MCS=Mayo Clinic Score; PD=pharmacodynamics; PK=pharmacokinetic; PML=progressive multifocal leukoencephalopathy; PCDAI=Pediatric Crohn's Disease Activity Index; PUCAI=Pediatric Ulcerative Colitis Activity Index; Q4W=every 4 weeks; Q8W=every 8 weeks; TB=tuberculosis; UC=Ulcerative Colitis; Wk=week.

Note: All study assessments and blood draws are to be conducted prior to study drug administration.

a The time window for days etrolizumab is administered is  $\pm 1$  day.

b All assessments must be performed after obtaining informed consent.

c Day 1 of Week 0.

d These samples are only collected for patients receiving 3 mg/kg etrolizumab administration Q8W.

## Appendix 1a

### Schedule of Activities: Randomized Treatment Phase (Treatment Period) (cont.)

- e Conducted at the discretion of the investigator. Unscheduled visit represents a visit that is not per the Schedule of Assessments and is required for an adverse event or for potential relapse assessment. All indicated assessments are NOT performed at each unscheduled visit. Assessments should be symptom driven (e.g., only perform PML neurologic examination if patient reports symptoms suspected of PML; for disease worsening, infectious etiologies may be investigated if clinically indicated; and confirmation of clinical relapse is performed by the MCS assessment). Assessments corresponding to items noted in this column should be recorded on the eCRF.
- f On days etrolizumab is administered, perform prior to administration.
- g Administer a serum pregnancy test at screening for all postpubertal female patients. A urine test may be performed at other specified visits; however, if the urine test result is positive, a confirmatory serum test must be performed. Patients must be reminded throughout the study that that in case of a positive pregnancy test, administration of study drug will be stopped immediately. Do not administer etrolizumab unless the serum pregnancy test result is negative. A urine pregnancy test is only required in female patients at Tanner Stage 2 or greater, or after onset of menarche. The test must be performed on a fresh voided sample.
- h Not required if patient has a normal chest X-ray result within 3 months prior to screening.
- i Full physical examination required at screening; symptom-driven physical examination at all other timepoints indicated.
- j PML neurologic examination consists of the PML Subjective Checklist. Administer before other assessments, per [Appendix 7](#).
- k For patients with Crohn's disease only. Hematocrit, albumin, and erythrocyte sedimentation rate (ESR) will be collected to calculate the PCDAI score.
- l Not required if unscheduled visit leads to withdrawal and assessment previously conducted at unscheduled visit.
- m The following tests are acceptable screening assays for latent TB in this study: purified protein derivative (a tuberculin skin test reaction; e.g., Mantoux test), INF- $\gamma$  based test (e.g., QuantiFERON®-TB Gold).
- n Viral serology and detection tests include HIV test, hepatitis B and C serology, hepatitis B DNA and hepatitis C RNA (Amplicor). Patients must undergo screening for HBV and HCV. This includes testing for HBsAg, anti-HBc, and hepatitis C antibody. Enrolled patients who are hepatitis B core antibody positive should have hepatitis B DNA measured at these timepoints. Measurement of HCV RNA with use of the Amplicor assay is required when the patient has a known history of HCV antibody positivity with past documentation of undetectable HCV RNA, either with or without history of anti-viral treatment. Patients with newly diagnosed HCV antibody positivity are not eligible for this study and, therefore, do not require measurement of HCV RNA.
- o Will be retained in the Research Biosample Repository for possible genetic analysis.
- p Samples will be used for fecal calprotectin assay and culture and sensitivity testing; ova, parasites, and *Clostridium difficile* toxin testing.
- q Samples will be used for, but not limited to, fecal calprotectin and microbiota analysis.
- r On days that etrolizumab is administered, sample should be taken prior to administration. If no ADA sample is specified for a visit, a PK sample may be used for ADA analysis.

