### **3. STUDY DESIGN**

#### **3.1 DESCRIPTION OF THE STUDY**

This pediatric PK/PD study consists of multiple phases. The randomized treatment phase is an open-label, randomized phase in which etrolizumab is administered to patients on the basis of body weight (mg/kg); randomization will be stratified by weight (<40 kg, ≥40 kg). Patients will be randomized in a 1:1 ratio to receive either high-frequency etrolizumab once every 4 weeks (Q4W) or low-frequency etrolizumab once every 8 weeks (Q8W). The high-frequency dose of 1.5 mg/kg etrolizumab will be administered Q4W (Weeks 0, 4, 8, and 12). The low-frequency dose of 3.0 mg/kg etrolizumab will be administered Q8W (Weeks 0 and 8).

After the 24-week randomized treatment phase (which includes a 16-week treatment period and an 8-week safety follow-up period), patients will then have the option to participate in the 312-week OLE phase (treatment with etrolizumab 1.5 mg/kg will be administered Q4W). All patients who participate in the 24-week randomized treatment phase and the 312-week OLE phase *will enter the 12-week safety follow-up period (see Appendix 1d; no etrolizumab treatment) and will complete the safety surveillance PML-monitoring phase (see Appendix 1e; no etrolizumab treatment for a total of 104 weeks)*. All patients who choose not to enter the OLE phase after the 24-week randomized treatment phase will enter the 104-week PML monitoring phase.

Patients can enter the OLE phase after completion of the 24-week randomized treatment phase. If the last visit of the randomized treatment phase and Day 1 of the OLE phase occur on the same day, the assessments from the randomized treatment phase should be completed. The assessments from the randomized treatment phase can apply to the OLE assessments (i.e., the same assessments should not be repeated for the OLE).

The 104-week PML monitoring phase will consist of telephone calls approximately every 6 months (see [Appendix 7](#)) with administration of the PML Subjective Checklist. If there are any signs or symptoms suggestive of PML identified on this subjective checklist during the telephone call, the patient will be asked to come into the clinic for a neurologic examination. The PML Algorithm (see [Appendix 8](#)) will be followed for any suspected

case of PML, and any confirmed case of PML will be reported as a serious adverse event (see Section 5.4.2).

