#### **4.5.6 Laboratory, Biomarker, and Other Biological Samples**

Laboratory assessments will be performed as indicated on the Schedule of Assessments (see [Appendix 1](#)). All laboratory assessments will be sent to one or more central laboratories for analysis with the exception of CMV. If there is suspicion for clinically significant CMV colitis, a colonic biopsy sample should be sent for CMV evaluation,

which may be conducted locally depending on local requirements for the timing of the test result. Urine pregnancy testing will be conducted locally.

On days of study drug administration, laboratory samples should be drawn before the administration of study drug. Laboratory assessments will include the following:

- Hematology (hemoglobin, hematocrit, platelet count, RBC count, WBC count, absolute differential count [neutrophils, eosinophils, lymphocytes, monocytes, basophils, other cells], mean corpuscular volume, mean corpuscular hemoglobin, mean corpuscular hemoglobin concentration, and RBC distribution width)
- Serum chemistries, including liver function tests (sodium, potassium, chloride, bicarbonate, glucose, blood urea nitrogen, creatinine, calcium, phosphorus, magnesium, total and direct bilirubin, total protein, albumin, alanine aminotransferase, aspartate aminotransferase, lactate dehydrogenase, alkaline phosphatase, creatine phosphokinase, and uric acid)
- Urinalysis
- Tuberculosis: The PPD skin test and QuantiFERON-TB Gold are acceptable screening assays for latent *Mycobacterium TB* infection.
  - A positive PPD tuberculin skin test reaction is considered  $\geq 5$  mm. Patients with a history of *Bacille Calmette-Guerin* (BCG) vaccination should be screened using the QuantiFERON-TB Gold test only. An indeterminate QuantiFERON-TB Gold test should be repeated. A positive QuantiFERON-TB Gold test or two successive indeterminate QuantiFERON-TB Gold test results should be considered a positive diagnostic TB test. An indeterminate QuantiFERON-TB Gold test followed by a negative QuantiFERON-TB Gold test, should be considered a negative diagnostic TB test.
  - If a negative TB screening test has been documented within 3 months of screening, no new test is needed.

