### **5.1.1.3 Hepatic Effects**

#### **Background**

Liver toxicity has been reported with other drugs that target  $\alpha 4$  integrins (natalizumab) and  $\alpha 4\beta 7$  integrins (vedolizumab). Therefore, this potential risk is being monitored in all etrolizumab studies. In nonclinical chronic toxicology studies, no abnormalities

indicating liver toxicity with etrolizumab were observed. The risk in humans is currently unknown.

*From an overall review of safety data from completed studies in UC, there have been no cases of potential drug-induced liver injury that have been attributed to etrolizumab.*

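### Appendix 1a limits the Day 28 and Day 84 chemistry to Crohn's disease, so children with UC have no scheduled liver test between Day 1 and Day 56 or between Day 56 and Day 98

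*Combined protocol and SAP*

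**What the plan says.** In the Appendix 1a treatment-period table the chemistry row, flattened, reads "Chemistry x x f x k x f x k x x x e x l". Set against the column headers, the marks are screening, Day 1 (f), Day 28 (k), Day 56 (f), Day 84 (k), Day 98, Day 112, unscheduled (e) and early withdrawal (l).

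- Footnote k: "For patients with Crohn's disease only. Hematocrit, albumin, and erythrocyte sedimentation rate (ESR) will be collected to calculate the PCDAI score". It also sits on the ESR row. The hematology marks at Days 28 and 84 do not carry it.
- Footnote f: "On days etrolizumab is administered, perform prior to administration". The Day 1 and Day 56 samples are therefore pre-dose.
- Footnote e: assessments at unscheduled visits are at the investigator's discretion and driven by symptoms.
- Section 4.5.6 places the liver tests in one panel: "Serum chemistries, including liver function tests". No other row of the schedule contains them.
- Section 5.1.1.3, on hepatic effects: "Therefore, this potential risk is being monitored in all etrolizumab studies". It calls the risk in humans unknown, and it leaves liver-test timing to the schedule plus clinical indication.
- Section 5.2.3 makes potential drug-induced liver injury an event of special interest, defined through ALT or AST together with bilirubin or jaundice.
- In Appendix 1c the chemistry marks at OLE Weeks 4 and 8 carry footnote h, worded as footnote k. The hematology marks at those two visits carry it too.

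**The concern.** The restriction follows the needs of an activity index. The PCDAI uses hematocrit, ESR and albumin; the PUCAI (Appendix 2) has no laboratory item. As a side effect, a child with UC has no scheduled liver chemistry at Days 28 and 84, although hepatic effects are listed as an important potential risk (Section 5.1.1) and this is the first pediatric study of the drug (Section 1.4).

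Two things are at stake. The first is ascertainment: a short rise in ALT without symptoms is seen only if a scheduled sample falls on it. The second is interpretation: Section 6.6 summarizes laboratory results descriptively by regimen received, with UC and Crohn's patients together. If the two diseases are tested unequally often, the pooled frequency of abnormal values partly reflects how often patients were sampled.

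**Working it through.** The documents give no figure for the interval between liver tests, so there is none to reproduce. The check maps the schedule and then does simple arithmetic on it.

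**Inputs**

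- Doses (Section 3.1): Q4W at Weeks 0, 4, 8 and 12, that is Days 1, 28, 56 and 84; Q8W at Weeks 0 and 8, that is Days 1 and 56.
- Windows (Appendix 1a): ±1 day on dosing days, ±3 days on other study days. Day 1 is the reference day.
- Post-dose chemistry days, UC: 56, 98, 112.
- Post-dose chemistry days, Crohn's, if footnote k means the full panel: 28, 56, 84, 98, 112.
- Post-dose liver-test days, Crohn's, if footnote k means albumin only: 56, 98, 112, as in UC.

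**Step 1. Days from each dose to the next scheduled liver test** (windows in brackets)

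| Dose | UC | Crohn's, full-panel reading |
|---|---|---|
| Day 1, both arms | 56 − 1 = 55 (54–56) | 28 − 1 = 27 (Q4W 26–28, Q8W 24–30) |
| Day 28, Q4W only | 56 − 28 = 28 (26–30) | 56 − 28 = 28 (26–30) |
| Day 56, both arms | 98 − 56 = 42 (38–46) | 84 − 56 = 28 (Q4W 26–30, Q8W 24–32) |
| Day 84, Q4W only | 98 − 84 = 14 (10–18) | 98 − 84 = 14 (10–18) |

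On Q4W a child with UC receives the Day 28 dose inside the first gap and the Day 84 dose inside the second.

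**Step 2. Chance that a transient elevation meets a scheduled test**

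Assume onset uniform over Days 1 to 112 (length 111 days) and an elevation lasting L days. It is detected if a test day falls within L days after onset. The proportion is the total length of onset times within L days before some test, overlaps counted once, divided by 111. The documents give no duration or onset pattern, so L = 14 and L = 28 serve as a range.

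- L = 14, UC: onsets in 42–56, 84–98 and 98–112. (14 + 14 + 14)/111 = 42/111 = 38%.
- L = 14, Crohn's: the same plus 14–28 and 70–84. 70/111 = 63%.
- L = 28, UC: onsets in 28–56 and 70–112. (28 + 42)/111 = 70/111 = 63%.
- L = 28, Crohn's: the whole span. 111/111 = 100%.

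Restricting onset to Days 1 to 56 (55 days): L = 14 gives 14/55 = 25% in UC and 28/55 = 51% in Crohn's; L = 28 gives 28/55 = 51% and 55/55 = 100%.

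On the albumin-only reading the Crohn's figures equal the UC figures: 38% and 38%, 63% and 63%.

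**Step 3. Are draws already scheduled?**

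At Days 28 and 84, hematology, PK and ADA samples are marked for all patients, so UC children are bled then anyway. At OLE Weeks 4 and 8 the laboratory marks are hematology, ESR and chemistry, all under footnote h, plus a pregnancy test that may be done on urine. UC children therefore have no routine blood draw at those visits. Their OLE chemistry runs from Week 0 to Week 12, with doses at Weeks 0, 4 and 8 before the Week 12 sample.

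**The case against.** The strongest reply is that the plan does not contradict itself outright. Section 5.1.1.3 defers to the schedule and to clinical indication, and the schedule does give UC children chemistry at screening and on Days 1, 56, 98 and 112. Adverse events are sought at visits in between, and unscheduled chemistry is possible. The same section reports no drug-induced liver injury attributed to etrolizumab in the completed UC studies, and no liver signal in nonclinical toxicology. The durations and uniform onset in the working are assumptions.

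Much of this stands, and it limits how far the point goes. A reader might infer more than the documents support:

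- That UC children have no liver test at all for eight weeks. What is absent is a scheduled post-dose test: a Day 1 pre-dose sample exists, and clinically indicated tests are allowed.
- That the problem belongs to the Q8W arm, with nothing within six weeks of any dose. Day 98 is exactly 42 days after Day 56 and can be 38 with windows, and Q4W children with UC have the same two gaps.
- That results by regimen are biased. Both arms follow the same chemistry days. Testing would differ by regimen only through a chance UC/Crohn's imbalance, which is possible because randomization is stratified by weight alone (Section 4.2), but is not built in.
- That sampling misses the period of risk because drug levels have fallen by then. Nothing in the documents links hepatic effects to serum level, and Sections 3.3.1 and 3.3.2 describe target-mediated, nonlinear kinetics that simple decay from an adult half-life would ignore.
- That UC children are certainly tested less than Crohn's children. Footnote k names only hematocrit, albumin and ESR, so the contrast depends on an unresolved reading.

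The reply does not remove the gap. Adult experience does not settle a first pediatric exposure, and symptom-driven testing does not find a rise without symptoms.

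**Conclusion.** The point holds for scheduled post-dose liver tests in the randomized phase. As printed, UC children in either arm have none between the Day 1 and Day 56 pre-dose samples (55 days) and none between Day 56 and Day 98 (42 days nominal, 38 to 46 with windows). This rests only on the table and its footnotes.

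The difference between diseases is conditional. If footnote k means the full panel, there are five post-dose test days in Crohn's disease and three in UC, and the detection figures of 38% v 63% (14 days) and 63% v 100% (28 days) illustrate its size under uniform onset. If it means albumin only, there is no contrast and both diseases have the UC gap. Either way the footnote needs clarifying. This is an inexpensive improvement to safety ascertainment and does not affect the primary PK and PD objective.

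**What to change.** 1. State in footnote k whether the Day 28 and Day 84 chemistry is the full panel or albumin alone, and reconcile it with the hepatic monitoring text in Sections 5.1.1.3 and 5.2.3.
2. Let the Day 28 and Day 84 chemistry panel, including liver tests, apply to both disease groups, using the draws already scheduled for all patients. Keep the Crohn's-only restriction on the ESR row. The longest interval from a dose to the next scheduled liver test then becomes 28 days nominal in both diseases.
3. For OLE Weeks 4 and 8, reconcile footnote h, on both hematology and chemistry, with Section 5.1.1.3. No added test is asked for there, because it would mean new blood draws for UC children.

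Cost: up to two extra panels per child with UC in the randomized phase (and the liver tests for Crohn's children at the same visits, if albumin alone was intended), with a little more blood. The volume should be checked against the limits cited in Section 4.5.6, since children from 13 kg are eligible. No change to dosing, stopping or treatment rules is implied.
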